3.1. Blinded Treatment Phase

Subjects who qualify for enrollment into the phase-2 portion of the study will be randomized in a 1:1 ratio to receive study treatment of EP with placebo or EP with tarextumab. The randomization will be balanced on the choice of platinum therapy (cisplatin versus carboplatin) and the prior use of whole brain radiation (WBR) or prophylactic cranial irradiation (PCI). Changing the choice of platinum therapy is not permitted once the subject is randomized. Treatment for each subject will begin on Cycle 1, Day 1 (the first dosing day). Etoposide 100 mg/m² will be given on Days 1, 2 and 3 and cisplatin 75 mg/m² or carboplatin to an AUC of 5 mg/mL/min will be given on Day 1 of every 21-day cycle for 6 cycles. Subjects may remain in the blinded treatment phase to continue one of the chemotherapy drugs if the other is held or discontinued prior to completing 6 cycles of EP and prior to disease progression. For subjects who have study drug held or discontinued for tolerability reasons, EP chemotherapy should continue to the completion of 6 cycles. Subjects may continue study drug if one or both of the chemotherapy drugs is held or discontinued prior to completing 6 cycles of EP and prior to disease progression.

After the completion of 6 cycles of EP, subjects who do not have disease progression and have not had WBR or PCI prior to study entry and are good candidates for PCI according to the

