5.2. Baseline Values

Unless otherwise noted, baseline is defined as the last non-missing value recorded prior to the first dose of study drug. Therefore, data collected during any unscheduled visits will be used in the determination of baseline values, as applicable.

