6.1. Analysis Populations

The following five groups of study patients will be used for statistical analyses.

1. The ITT patient population includes all patients randomized to receive study drug regardless of whether they actually received study drug and regardless of whether evidence is found indicating they failed to meet study inclusion/exclusion criteria or had other protocol violations. When the ITT patient population is analyzed, patients are grouped according to

their randomized treatment regardless of actual treatment received. The ITT patient population is the analysis population for demographics and baseline characteristics and for all statistical inference and primary tests of hypotheses related to efficacy endpoints.

2. The safety patient population is the subset of ITT patients who received at least one dose of study drug. When the safety patient population is analyzed, patients are grouped according to actual treatment received. Tarextumab is considered a patient's "treatment received" in the safety patient population if the patient received at least one dose of tarextumab (complete or incomplete dose) any time during the study. The safety patient population is the analysis population for all analyses of safety data.
3. The per-protocol (PP) patient population is the subset of safety patients who either (a) have at least one response evaluation on study, or (b) die prior to their first scheduled response evaluation. When the per-protocol patient population is analyzed, patients are grouped according to actual treatment received. The per-protocol population is used for sensitivity (secondary, supportive) analyses of efficacy endpoints.
4. The pharmacokinetic (PK) patient population is comprised of all subjects who received at least one complete dose of tarextumab and have at least one post-dose PK sample.
5. The immunogenicity patient population is comprised of all subjects who had a baseline and one or more follow-up samples obtained for quantifying anti-tarextumab antibody.

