11.7. Immunogenicity

The incidence of anti-tarextumab antibody development in the tarextumab treatment group will be summarized with counts and proportions. In addition, the impact of detectable anti-tarextumab antibodies and neutralizing anti-tarextumab antibodies on the efficacy of tarextumab will be assessed by summarizing PFS and OS in the subgroups of patients with and without these anti-tarextumab antibodies. The impact of detectable anti-tarextumab antibodies and neutralizing anti-tarextumab antibodies on the safety of tarextumab will be assessed by comparing AE incidence rates in the subgroups of patients with and without these anti-tarextumab antibodies. However, these subgroup analyses may not be carried out if the number of subjects with or without anti-tarextumab antibodies does not provide reasonable estimates of PFS and ORR.

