Note: SBP=Systolic Blood Pressure. DBP=Diastolic Blood Pressure. Normal Range Temperature: 36.6°C to 37.3°C. Normal Range SBP: 90-120 mmHg. Normal Range DBP: 60-80 mmHg. Normal Range Respiratory Rate: 12-18 breaths per minute. Normal Range Pulse Rate: 60-100 beats per minute.

^[1] Each subject is represented once by their worst change. A range change can be either a change in a vital sign parameter value from baseline low or normal to post-baseline high or a change from baseline high or normal to post-baseline low. A subject can be included in both 'High' and 'Low' categories if applicable.

Table 14.3.4.16
12-Lead Electrocardiogram (ECG)
Safety Population

Parameter	Time Point	Placebo (N=xx)		Tarextumab (N=xx)	
		Result	Change from Baseline	Result	Change from Baseline
QRS Duration (msec)	Baseline ^[1]				
	n	xx		xx	
	Mean (SD)	xx.x (xx.xx)		xx.x (xx.xx)	
	Median	xx		xx	
	25 th , 75 th Percentile	xx, xx		xx, xx	
	Min, Max	xx, xx		xx, xx	
Maximum Post-Baseline	n	xx	xx	xx	xx
	Mean (SD)	xx.x (xx.xx)	xx.x (xx.xx)	xx.x (xx.xx)	xx.x (xx.xx)
	Median	xx	xx	xx	xx
	25 th , 75 th Percentile	xx, xx	xx, xx	xx, xx	xx, xx
	Min, Max	xx, xx	xx, xx	xx, xx	xx, xx
Minimum Post-Baseline	n	xx	xx	xx	xx
	Mean (SD)	xx.x (xx.xx)	xx.x (xx.xx)	xx.x (xx.xx)	xx.x (xx.xx)
	Median	xx	xx	xx	xx
	25 th , 75 th Percentile	xx, xx	xx, xx	xx, xx	xx, xx
	Min, Max	xx, xx	xx, xx	xx, xx	xx, xx
Last Observation Post-Baseline	n	xx	xx	xx	xx
	Mean (SD)	xx.x (xx.xx)	xx.x (xx.xx)	xx.x (xx.xx)	xx.x (xx.xx)
	Median	xx	xx	xx	xx
	25 th , 75 th Percentile	xx, xx	xx, xx	xx, xx	xx, xx
	Min, Max	xx, xx	xx, xx	xx, xx	xx, xx
PR Interval (msec)	Baseline ^[1]				
	[etcetera]	[:]	[:]	[:]	[:]

^[1] Baseline is defined as the last non-missing value prior to first dose of study drug.

Programmer notes: (a) continue for all electrocardiogram parameters (QRS duration, PR interval, QTc Interval)

Table 14.3.4.17
12-Lead Electrocardiogram (ECG) – Range Change Abnormal
Safety Population

ECG Parameter	Placebo (N=xx)	Tarextumab (N=xx)
n	xx	xx
Any Post-Baseline High ^[1]		
QRS Duration (msec)	xx (xx.x%)	xx (xx.x%)
PR Interval (msec)	xx (xx.x%)	xx (xx.x%)
QTc Interval (msec)	xx (xx.x%)	xx (xx.x%)
Low ^[1]		
QRS Duration (msec)	xx (xx.x%)	xx (xx.x%)
PR Interval (msec)	xx (xx.x%)	xx (xx.x%)
QTc Interval (msec)	xx (xx.x%)	xx (xx.x%)
Last Observation Post-Baseline High ^[1]		
QRS Duration (msec)	xx (xx.x%)	xx (xx.x%)
PR Interval (msec)	xx (xx.x%)	xx (xx.x%)
QTc Interval (msec)	xx (xx.x%)	xx (xx.x%)
Low ^[1]		

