	Abnormal - Clinically Significant	xx (xx.x%)	xx (xx.x%)

^[1] Baseline is defined as the last non-missing value prior to first dose of study drug.

Table 14.3.4.21
ECOG Performance Status
Safety Population

Performance Status Score ^[1]	Placebo (N=xx)	Tarextumab (N=xx)
Baseline ^[2]		
n	xx	xx
0	xx (xx.x%)	xx (xx.x%)
1	xx (xx.x%)	xx (xx.x%)
2	xx (xx.x%)	xx (xx.x%)
3	xx (xx.x%)	xx (xx.x%)
4	xx (xx.x%)	xx (xx.x%)
5	xx (xx.x%)	xx (xx.x%)
Maximum Post-Baseline		
n	xx	xx
0	xx (xx.x%)	xx (xx.x%)
1	xx (xx.x%)	xx (xx.x%)
2	xx (xx.x%)	xx (xx.x%)
3	xx (xx.x%)	xx (xx.x%)
4	xx (xx.x%)	xx (xx.x%)
5	xx (xx.x%)	xx (xx.x%)
Minimum Post-Baseline		
n	xx	xx
0	xx (xx.x%)	xx (xx.x%)
1	xx (xx.x%)	xx (xx.x%)
2	xx (xx.x%)	xx (xx.x%)
3	xx (xx.x%)	xx (xx.x%)
4	xx (xx.x%)	xx (xx.x%)
5	xx (xx.x%)	xx (xx.x%)
Last Observation Post-Baseline		
n	xx	xx
0	xx (xx.x%)	xx (xx.x%)
1	xx (xx.x%)	xx (xx.x%)
2	xx (xx.x%)	xx (xx.x%)
3	xx (xx.x%)	xx (xx.x%)
4	xx (xx.x%)	xx (xx.x%)
5	xx (xx.x%)	xx (xx.x%)

Note: Percentages are based on the number of patients with a non-missing response at each visit.

^[1] For complete definitions of each activity status code, reference Appendix D of the clinical protocol.

^[2] Baseline is defined as the last non-missing value prior to first dose of study drug.

Table 14.3.4.22
ECOG Performance Status – Shift from Baseline
Safety Population

Performance Status Score ^[1]	Placebo (N=) Baseline ^[2]		Tarextumab (N=) Baseline ^[2]	
	0	1	0	1
Maximum Post-Baseline				
n	n (%)	n (%)	n (%)	n (%)
0	n (%)	n (%)	n (%)	n (%)
1	n (%)	n (%)	n (%)	n (%)
2	n (%)	n (%)	n (%)	n (%)
3	n (%)	n (%)	n (%)	n (%)
4	n (%)	n (%)	n (%)	n (%)
5	n (%)	n (%)	n (%)	n (%)
Minimum Post-Baseline				
n	n (%)	n (%)	n (%)	n (%)
0	n (%)	n (%)	n (%)	n (%)
1	n (%)	n (%)	n (%)	n (%)
2	n (%)	n (%)	n (%)	n (%)
3	n (%)	n (%)	n (%)	n (%)
4	n (%)	n (%)	n (%)	n (%)
5	n (%)	n (%)	n (%)	n (%)

^[1] For complete definitions of each activity status code, reference Appendix D of the clinical protocol.

^[2] Baseline is defined as the last non-missing value prior to first dose of study drug.

Programming note: Continue for Last Observation Post-Baseline.

Programming note: Add additional baseline columns as needed.

Table 14.3.4.23
Anti-Tarextumab Antibodies
Immunogenicity Population

Time Point	Tarextumab (N=xx)
Any Positive Sample During Study	xx (xx.x%)
Cycle 1, Day 1	
Positive	xx (xx.x%)
Negative	xx (xx.x%)
Viable Sample Not Available	xx (xx.x%)
Cycle 3, Day 1	
Positive	xx (xx.x%)
Negative	xx (xx.x%)

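### The headline row of the anti-tarextumab antibody table has no post-baseline limit, so it does not measure the antibody development that SAP section 11.7 promises

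*SAP*

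**What the plan says.** Immunogenicity is a secondary objective (SAP section 2.2). Section 11.7 states the measure: "The incidence of anti-tarextumab antibody development in the tarextumab treatment group will be summarized with counts and proportions".

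The only table for that incidence is the shell of Table 14.3.4.23 in Appendix B. It has a single tarextumab column and opens with the row "Any Positive Sample During Study". Beneath it are positive, negative and no-viable-sample rows for four time points: Cycle 1 Day 1, Cycle 3 Day 1, Cycle 5 Day 1 and treatment termination. The shell has no footnote or programmer note.

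Three other places bear on how the row is read:

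- Section 3.1 fixes the start of dosing: "Treatment for each subject will begin on Cycle 1, Day 1 (the first dosing day").
- Section 5.2 sets the general rule that "baseline is defined as the last non-missing value recorded prior to the first dose of study drug".
- Section 6.1 defines the immunogenicity population as "all subjects who had a baseline and one or more follow-up samples obtained for quantifying anti-tarextumab antibody".

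For the antibody subgroups, section 11.7 plans to assess the impact of detectable and neutralizing antibodies by "summarizing PFS and OS in the subgroups of patients with and without these anti-tarextumab antibodies", and by comparing adverse event rates in the same way. The shells are Tables 14.3.4.24 to 14.3.4.27.

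**The concern.** Development means a change after exposure. A row that counts any positive sample also counts antibody, or assay reactivity, that was there before the first infusion. A patient positive at Cycle 1 Day 1 and negative at every later sample would add to the reported incidence although nothing developed.

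The population definition requires a baseline and a follow-up sample from every member, which is what is needed to tell pre-existing from new antibody. The headline row does not use that pairing, and the SAP nowhere says how a baseline-positive patient is classed.

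At stake is whether the proportion reported for a secondary objective is the one the text promises. A reader who takes it as the immunogenicity rate of the drug would take it too high whenever any patient is positive at baseline.

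**Working it through.** **Step 1. Text against shell.** The SAP states no antibody rate and no sample size for immunogenicity, so there is no figure to reproduce.

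| Element | Section 11.7 | Table 14.3.4.23, headline row |
|---|---|---|
| What is counted | antibody development | any positive sample in the study |
| Post-baseline limit | implied by development | none |
| Baseline-positive patients | no rule | counted, on the plain wording |
| Denominator | not stated | N of the table (immunogenicity population) |

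**Step 2. Comparison with other safety outputs.** Elsewhere the SAP writes the restriction in. The vital-sign and ECG range-change shells (Tables 14.3.4.15 and 14.3.4.17) use the row label "Any Post-Baseline High" and require a change from baseline. The laboratory shift and CTCAE grade tables count only movement from baseline. Section 11.2 requires a treatment-emergent adverse event to start or worsen after the first study drug dose. The antibody table has no equivalent.

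**Step 3. Is Cycle 1 Day 1 the baseline sample?** The SAP does not say so. It is inferred: Cycle 1 Day 1 is the first dosing day, the population requires a baseline sample, and none of the other three listed time points can be one. Listing 16.2.8.11 also shows a screening visit, but a screening sample would be pre-treatment too.

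**Step 4. Size of the excess.** Let

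- A = patients with any positive sample (the headline count),
- B = patients positive at baseline, whatever their later status,
- D = patients negative at baseline and positive later (development).

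Every patient in A is in exactly one of B or D, so A = B + D and the excess is A − D = B.

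**Step 5. Illustration.** Inputs: 134 patients (planned enrolment, SAP Table 2) randomized 1:1 (section 3.1), giving 134/2 = 67. Assumed, because the SAP gives neither: b, the share positive at baseline, and e, the share of baseline-negative patients who become positive. Then B = 67b, D = 67(1 − b)e, and the headline proportion is 1 − (1 − b)(1 − e).

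| b | B | D (e = 5%) | Headline (e = 5%) | D (e = 10%) | Headline (e = 10%) |
|---|---|---|---|---|---|
| 0% | 0 | 3.4 | 5.0% | 6.7 | 10.0% |
| 2% | 1.3 | 3.3 | 6.9% | 6.6 | 11.8% |
| 5% | 3.4 | 3.2 | 9.75% | 6.4 | 14.5% |
| 10% | 6.7 | 3.0 | 14.5% | 6.0 | 19.0% |

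A row limited to baseline-negative patients would read 5% or 10% throughout.

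The figure of 67 is itself approximate. The model note under SAP Table 6 implies 89 + 56 = 145 patients, or about 72 per arm, and 72 × 0.02 = 1.4 and 72 × 0.10 = 7.2. The true denominator is the immunogenicity population, whose size is not given.

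**Step 6. What the printed table still allows.** From A = B + D, D = A − B. If Cycle 1 Day 1 is the baseline, B is printed as the Cycle 1 Day 1 positive row, and a patient positive both then and later cancels. The baseline-negative denominator is the Cycle 1 Day 1 negative row. With b = 10% and e = 5%: 9.7 − 6.7 = 3.0, over 67 × 0.90 = 60.3, which is 5.0%. The result is only approximate where the Cycle 1 Day 1 sample is not viable or the baseline was drawn at another visit. How many baseline-positive patients were positive or negative later cannot be recovered.

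**The case against.** The best reply is that the table is labelled loosely but hides nothing. Cycle 1 Day 1 positivity is printed directly under the headline, and one subtraction gives the newly positive count. That stands, with the limits in step 6, and it means a reader should not infer that antibody development cannot be determined from the table. It does not rescue the headline: the proportion actually printed, and its denominator, are those of a different quantity.

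A second reply is that the reading is inferred. The shell does not say that Cycle 1 Day 1 feeds the headline row or that the sample is pre-dose; a programmer could apply the word development from section 11.7; and sampling times may be in the protocol, which is not shown. This is fair and lowers certainty. Still, the literal wording of the row includes every listed sample, and other shells state the post-baseline limit when they mean it.

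A third concerns Tables 14.3.4.24 to 14.3.4.27. A reader might infer that the PFS, OS and adverse event comparisons are corrupted by pre-existing reactivity. The SAP does not support that. Nothing says those columns take their status from the headline row, and section 11.7 defines the subgroups by detectable antibody, which a pre-existing antibody satisfies. Imposing treatment-emergent status there would be a preference, not a correction. What remains is that these shells do not say how a baseline-positive patient is classed. Section 11.7 also allows the subgroup analyses to be dropped if numbers are too small.

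**Conclusion.** The point holds as a mismatch between a stated measure and the row meant to report it. Followed literally, the row exceeds antibody development by exactly the number of baseline-positive patients.

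How large that is cannot be said from the SAP. It is zero if no patient is positive at baseline, and about 1 to 7 of roughly 67 if 2% to 10% are; those rates are assumptions. A reader might infer from the illustration that the incidence will be inflated two- or threefold. That happens only at the upper assumed baseline rates combined with low true development, and the SAP supports neither figure.

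The conclusion rests on two inferences: that the Cycle 1 Day 1 sample is taken before dosing, and that the headline row pools all listed time points. It concerns a descriptive, single-arm secondary summary with no test or decision rule attached. The primary PFS analysis is unaffected.

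**What to change.** In section 11.7 and Table 14.3.4.23:

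- Make the headline row antibody development, defined as a negative baseline sample and at least one positive post-dose sample.
- Use baseline-negative patients with at least one follow-up sample as its denominator.
- State which sample is the baseline, and how a patient without a viable baseline result is handled.
- Report baseline-positive patients on a separate row, split by later status, with a stated rule for any whose antibody level rises after dosing. A definition confined to baseline-negative patients leaves that case open.

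In Tables 14.3.4.24 to 14.3.4.27, keep the detectable-antibody subgroups of section 11.7 and add a footnote saying how baseline-positive patients are classed.

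The cost is SAP wording, two or three shell rows and footnotes. The population definition already requires the samples, so no new data are needed. The headline denominator shrinks by the number of baseline-positive patients.

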APPENDIX C. FIGURE SHELLS

Figure 14.2.1.1
Overall Survival
ITT Population

Programmer notes: (a) replace "Treatment A" with "Placebo"; (b) replace "Treatment B" with "Tarextumab"; (c) include "at risk" counts beneath the x-axis (see secondary figure mock below); (d) delete "Treatment C"; (e) duplicate figure using per-protocol population and all gene-expression subsets of the ITT population; (f) duplicate figure for progression-free survival using the ITT population; (g) duplicate figure for overall survival using the per-protocol population and all gene-expression subsets of the ITT population

Secondary figure mock showing format for “at risk” summary:

[figure not shown]
[figure not shown]
[figure not shown]

Figure 14.2.4.1
Waterfall Plot of Best Percentage Change from Baseline Total Tumor Length
ITT Population

Programmer notes: (a) replace "screening" in the y-axis label with "Baseline"; (b) delete the footnote marker "[1]" from the y-axis label; (c) duplicate figure using per-protocol population

Figure 14.3.4.63
Box Plot of Pulse Rate by Visit
Safety Population

Programmer notes: (a) replace “Cohort 1” with “Placebo”; (b) replace “Cohort 2” with “Tarextumab”; (c) delete “Cohort 3” and “Cohort 4”; (d) duplicate figure for all clinical laboratory, vital sign and ECG parameters (see Planned Tables, Figures and Listings [Appendix A] for complete list); (e) duplicate all figures for “Box Plot of Change from Baseline Parameter by Visit” – remember to (i) remove the “Baseline” marker from the x-axis and (ii) replace the y-axis label “Parameter (unit)” with “Change from Baseline Parameter (unit)”

APPENDIX D. LISTING SHELLS

**Listing 16.2.1.1
Subject Disposition**

Treatment Group	Subject ID	ITT Population	Per-Protocol Population	Safety Population		Immunogenicity Population		Pharmacokinetic Population		Treatment Start Date	Treatment End Date	Primary Reason for Ending Study Treatment		Study Exit Date	Primary Reason for Study Exit	
				Y	N	Y	N	Y	N							
Placebo Tarextumab	003-xxx-xxx	Y N	Y N	Y N	Y N	Y N	Y N	Y N	Y N	ddmmmyyy	ddmmmyyy	Lost to follow-up Withdrawal of consent/Patient decision Death	Lost to Follow-Up Study Terminated by OncoMed Withdrawal by Subject Other: Other term	ddmmmyyy	Death	Lost to Follow-Up Study Terminated by OncoMed Withdrawal by Subject Other: Other term

OncoMed Pharmaceuticals, Inc.
59R5-003 (Phase 2)

Page 1 of x

Listing 16.2.1.2
Informed Consent

Treatment Group	Subject ID	Informed Consent Date	Randomization Date	Consented to Optional Tumor Biopsy	If Yes, Date Optional Tumor Biopsy Consent Date	Consented to Optional Pharmacogenomics Blood Sample	If Yes, Optional Pharmacogenomics Blood Sample Consent Date	Consented to DNA Testing on Blood Sample	If Yes, DNA Testing on Blood Sample Consent Date	Consented to DNA Testing on Tumor Tissue Sample	If Yes, DNA Testing on Tumor Tissue Sample Consent Date
Placebo Tarixumab	003-xxx-xxx	ddmmmyyy	ddmmmyyy	Yes No	ddmmmyyy	Yes No	ddmmmyyy	Yes No	ddmmmyyy	Yes No	ddmmmyyy

**Listing 16.2.2.1
Major Protocol Deviations**

Treatment Group	Subject ID	Protocol Deviation Description	Deviation Code
Placebo Tarextumab	003-xxx-xxx	Description	xx-Deviation Code

Listing 16.2.3.1
Inclusion/Exclusion Criteria

Treatment Group	Subject ID	Protocol Version Date	Did the subject meet all eligibility criteria? Yes No	Criteria Type		Criterion Number	Reason Not Met Reason
				Inclusion Exclusion	None		
Placebo Tarextumab	003-xxx-xxx	ddmmmyyy				xx	

Programmer notes: (a) all subjects should be listed; (b) Display “None” for Criteria Type as appropriate

Treatment Group	Subject ID	Date of Birth	Age (years) ^[1]	Sex	If Female, Child-Bearing Potential?	Race	Ethnicity
Placebo Tarextumab	003-xxx-xxx	ddmmmyyy	xx.x	Male Female	Yes No	American Indian or Alaska Native Asian Black or African American Native Hawaiian or Other Pacific Islander White	Hispanic or Latino Not Hispanic or Latino

<second part of listing>

Treatment Group	Subject ID	Height (cm)	Weight (kg)	Body Mass Index ^[2] (mg/m ²)	ECOG	Smoking History	If Ex-Smoker or Current Smoker, number of pack years	If Ex-Smoker, Stop Date
Placebo Tarextumab	003-xxx-xxx	xxx	xx.x	x.xx	0 1 2	Never Smoked Ex Smoker Current Smoker	xx	ddmmmyyy

^[1] Age at time informed consent was signed.
^[2] BMI (kg/m²) = weight (kg) / [height (cm)]².

Listing 16.2.4.2 Medical/Surgical History					
Treatment Group	Subject ID	Any past and/or concomitant diseases or past surgeries?	Description of Medical Condition/Event	Onset Date	End Date
Placebo Tarextumab	003-xxx-xxx	Yes No	Description	ddmmyyyy	ddmmyyyy
					Ongoing/ Resolved
					Ongoing Resolved

Listing 16.2.4.3
Extensive Small Cell Lung Cancer History

Treatment Group	Subject ID	Date of Diagnosis (Study Day)	Months Since Diagnosis	Histological/Cytological Type	Anatomical Location of Primary Cancer	Number of Sites of Disease at Study Entry	Sites of Disease at Study Entry
Placebo Tarextumab	003-xxx-xxx	ddmmmyyy (xx)	xx	Small Cell	Right Upper Lung	x	Bone Brain:
				Only	Right Lower Lung		Symptomatic/
				Mixed Type	Middle of Right		Asymptomatic
				Other:	Lung		Pleura Adrenal Gland
				Other term	Left Upper Lung		Lymph Nodes: Specify
					Other: Other term		Lymph Nodes
							Other Nodes: Other location

Programmer notes: (a) for Sites of Disease at Study Entry, list all that apply

Listing 16.2.4.4
Prior Surgery for Lung Cancer

Treatment Group	Subject ID	Prior Surgery for Lung Cancer Yes No	Surgery Date ddmmmyyy	Description of Surgery	
				Description	Location
Placebo Tarextumab	003-xxx-xxx				

Listing 16.2.4.5
Prior Radiotherapy for Lung Cancer

Treatment Group	Subject ID	Prior Radiotherapy for Lung Cancer		Start Date	End Date	Site of Treatment	Total cGY
		Yes	No				
Placebo Tarextumab	003-xxx-xxx			ddmmmyyy	ddmmmyyy	Site of Treatment	xx Unknown

Listing 16.2.4.6
Baseline Gene Expression

Treatment Group	Subject ID	Notch3 Expression	Hes1 Expression	Hey1 Expression	Hey2 Expression	Hes6 Expression
Placebo Tarextumab	003-xxx-xxx	Yes No	Yes No	Yes No	Yes No	Yes No

Listing 16.2.4.7
FFPE Tissue Sample
Part 1 of 2

Archival Tissue					
Treatment Group	Subject ID	Sample submitted?	Biopsy Date (Study Day)	Date of Submission to OncoMed (Study Day)	
				Yes	No
Placebo Tarextumab	003-xxx-xxx	Yes No	ddmmmyyyy (xx)	ddmmmyyyy (xx)	Liver Lymph Nodes Peritoneum Chest Wall Abdomen Pelvis Breast Skin Kidney Lung Other: Other organ

[1] If archival tissue was not submitted.
<second part of listing>

Listing 16.2.4.7
FFPE Tissue Sample
Part 2 of 2

Fresh Tumor Core Biopsies					
Treatment Group	Subject ID	Biopsies Performed? ^[1]	Biopsies Date (Study Day)	Date of Submission to OncoMed (Study Day)	
				Yes	No
Placebo Tarextumab	003-xxx-xxx	Yes No	ddmmmyyyy (xx)	ddmmmyyyy (xx)	Liver Lymph Nodes Peritoneum Chest Wall Abdomen Pelvis Breast Skin Kidney Lung Other: Other organ

[1] If archival tissue was not submitted.

Listing 16.2.4.8
Prior and Concomitant Medications

Treatment Group	Subject ID	Verbatim Term //		Start Date (Study Day)	End Date (Study Day)	Route	Indication
		Preferred Name	ATC Class ^[1]				
Placebo Tarextumab	003-xxx-xxx	Verbatim Term //		ddmmmyyy (xx)	ddmmmyyy (xx) Ongoing	Inhalation Intra-arterial Intralesional Intramuscular Intraocular Intraperitoneal Intravenous Nasal Oral Rectal Subcutaneous Topical Transdermal Vaginal Other: Other term	Medical History #xx: MH term Adverse Event #xx: AE term Other: Other term
		Preferred Name	ATC Class				

[1] ATC Class and Preferred Name are coded using WHO Drug Dictionary Enhanced (version March 1, 2014).

Listing 16.2.4.9 Concomitant Procedures						
Treatment Group	Subject ID	Any Concomitant Procedures?	Procedure	Anatomical Location	Start Date (Study Day)	End Date (Study Day)
Placebo Tarextumab	003-xxx-xxx	Yes No	Procedure	Location	ddmmmyyyy (xx)	ddmmmyyyy (xx)
						Indication Medical History #xx: MH term Adverse Event #xx: AE term Other: Other term

OncoMed Pharmaceuticals, Inc.
59R5-003 (Phase 2)

Page 1 of x

Listing 16.2.5.1
Study Drug Infusion
Part 1 of 3: Infusion Administration

Treatment Group	Subject ID	Visit	Infusion Performed?	If Infusion Was Not Performed, Specify Reason	If AE, Specify	Date of Infusion (Study Day)	Infusion Start / Stop Times	Intended Dose Per Protocol (mg)	What Weight Was Used to Calculate Dose?	Infusion Dose (mg)
Placebo Tarxutumab	003-xxx-xxx	CYCLE X DAY X	Yes No	Adverse Event Other: Other term	AE term	ddmmmyyyy (xx)	xx:xx / xx:xx	xx.xx	Weight at Current Visit Weight at Baseline Other: Other term	xxxx

<second part of listing>

OncoMed Pharmaceuticals, Inc.
59R5-003 (Phase 2)

Page 1 of x

Listing 16.2.5.1
Study Drug Infusion
Part 2 of 3: Infusion Reduced or Delayed

Treatment Group	Subject ID	Visit	Dose Reduced			Infusion Delayed		
			Dose reduced since last infusion?	Specify Reason	If AE, Specify	Infusion Delayed?	Specify Reason	If AE, Specify
Placebo Tarxutumab	003-xxx-xxx	CYCLE X DAY X	Yes No	Adverse Event Other: Other term	AE term	Yes No	Adverse Event Other: Other term	AE term

<third part of listing on next page>

OncoMed Pharmaceuticals, Inc.
59R5-003 (Phase 2)

Page 1 of x

Listing 16.2.5.1
Study Drug Infusion
Part 3 of 3: Infusion Interrupted or Restarted

Treatment Group	Subject ID	Visit	Infusion Interrupted			Restart after Interruption			Total Dose Administered (mg)
			Infusion Interrupted?	Specify Reason	If AE, Specify	Infusion Restarted?	Start / Stop Times	Completed After Restart	
Placebo Tarxutumab	003-xxx-xxx	CYCLE X DAY X	Yes No	Adverse Event Other: Other term	AE term	Yes No	xx:xx / xx:xx	Infusion was completed Infusion was interrupted again	xxxx

OncoMed Pharmaceuticals, Inc.
59R5-003 (Phase 2)

Page 1 of x

Listing 16.2.5.2
Etoposide Infusion
Part 1 of 3: Infusion Administration

Treatment Group	Subject ID	Visit	Infusion Performed?	If Infusion Was Not Performed, Specify Reason	If AE, Specify	Date of Infusion (Study Day)	Infusion Start / Stop Times	Intended Dose Per Protocol (mg)	What Weight Was Used to Calculate Dose?	BSA (m ²)	Actual Dose (mg)
Placebo Tarextumab	003-xxx-xxx	CYCLE X DAY X	Yes No	Adverse Event Other: Other term	AE term	ddmmmyyy (xx)	xx:xx / xx:xx	xx.xx	Weight at Current Visit Weight at Baseline Other: Other term	xx	xxxx

<second part of listing>

OncoMed Pharmaceuticals, Inc.
59R5-003 (Phase 2)

Page 1 of x

Listing 16.2.5.2
Etoposide Infusion
Part 2 of 3: Infusion Reduced or Delayed

Treatment Group	Subject ID	Visit	Dose reduced since last infusion?		Dose Reduced		Infusion Delayed		If AE, Specify	Specify Reason	Adverse Event Other: Other term	Specify	If AE, Specify
			Yes	No	Yes	No	Yes	No					
Placebo Tarextumab	003-xxx-xxx	CYCLE X DAY X	X		X		X						

<third part of listing>

OncoMed Pharmaceuticals, Inc.
59R5-003 (Phase 2)

Page 1 of x

Listing 16.2.5.2
Etoposide Infusion
Part 3 of 3: Infusion Interrupted or Restarted

Treatment Group	Subject ID	Visit	Infusion Interrupted?		Infusion Interrupted		Restart after Interruption		Total Dose Administered (mg)	
			Yes	No	Specify Reason	Adverse Event Other: Other term	Infusion Restarted?	Start / Stop Times	Completed After Restart	
Placebo Tarextumab	003-xxx-xxx	CYCLE X DAY X	X		X		Yes No	xx:xx / xx:xx	Infusion was completed Infusion was interrupted again	xxxx

Treatment Group	Subject ID	Visit	CYCLE X DAY X	Infusion Performed?	If Yes, Specify therapy	If Infusion Was Not Performed, Specify Reason	If AE, Specify AE term	Date of Infusion (Study Day)	Infusion Start / Stop Times	Intended Dose Per Protocol	What Weight Was Used to Calculate Dose?	BSA (m ²)	GFR (mL/min/1.73 m ²)	Actual Dose (mg)
Placebo Tarextumab	003-xxx-xxx	CYCLE X DAY X		Yes No	Cisplatin Carboplatin	Adverse Event Other term	AE term	ddmmmyyy (xx)	xx:xx / xx:xx	xx.xx mg/m ² xx.xx mg/mL-min	Weight at Current Visit Weight at Baseline Other: Other term	xx	xx	xxxx

<second part of listing>

Listing 16.2.5.3
Platinum Therapy Infusion
Part 2 of 3: Infusion Reduced or Delayed

Treatment Group	Subject ID	Visit	CYCLE X DAY X	Dose reduced since last infusion?		Dose Reduced		Infusion Delayed	
				Yes	No	Specify Reason	If AE, Specify AE term	Infusion Delayed?	If AE, Specify AE term
Placebo Tarextumab	003-xxx-xxx	CYCLE X DAY X		Yes	No	Adverse Event Other term	AE term	Yes No	Specify Reason Adverse Event Other: Other term

<third part of listing>

Listing 16.2.5.3
Platinum Therapy Infusion
Part 3 of 3: Infusion Interrupted or Restarted

Treatment Group	Subject ID	Visit	CYCLE X DAY X	Infusion Interrupted?		Infusion Interrupted		Restart after Interruption		Total Dose	
				Yes	No	Specify Reason	If AE, Specify AE term	Infusion Restarted?	Start / Stop Times	Completed After Restart	Planned Dose (mg)
Placebo Tarextumab	003-xxx-xxx	CYCLE X DAY X		Yes	No	Adverse Event Other: Other term	AE term	Yes No	xx:xx / xx:xx	Infusion was completed Infusion was interrupted again	xxxx

Listing 16.2.5.4
Doses Delayed, Interrupted, Reduced and Not Administered

Treatment Group	Subject ID	Visit	Date (Study Day)		Dosing	Reason	Adverse Event/Other Reason		
			Yes	No			Adverse Event	Other	Adverse Event #xx: AE term Other term
Placebo Tarextumab	003-xxx-xxx	CYCLE X DAY X	X						
					Dose Delayed				
					Dose Interrupted				
					Dose Reduced				
					Not Administered				

Note: This listing is sorted by Treatment, Dosing, Reason, and Subject.

Listing 16.2.5.5
Pre-dose, Post-dose and Single PK Samples

Treatment Group	Subject ID	Visit	Was PK Sample Drawn?	Draw Date (Study Day)	Time Point		Draw Time
					Pre-dose	Post-dose	
Placebo	003-xxx-xxx	SCREENING	Yes No	ddmmmyyyy (xx)			xx:xx
Tarextumab		CYCLE X DAY X				[blank]	

Listing 16.2.6.2
Tumor Evaluations – Target Lesions

Treatment Group	Subject ID	Visit	Was radiographic evaluation performed?	Date Performed (Study Day)	Location Number	Location	Location Description (Position within Organ)	Technique Used	Thickness of slice (mm) ^[1]	Longest Diameter (mm) ^[2]	Baseline Sum of Longest Diameters (mm)	Visit Sum of Longest Diameters (mm)	Percent Change from Baseline
Placebo	003-xxx-xxx	SCREENING	Yes No	ddmmmyyy	1 2 3, etc.	Pancreas	Position	MRI	xx.x	xx.x	[blank]	[blank]	[blank]
Tarextumab		CYCLE X DAY X		(xx)		Liver		Conventional CT		Unable to Evaluate			
						Lymph nodes		Spiral CT					
						Peritoneum		PET CT					
						Chest Wall		Bone Scan					
						Abdomen		Other:					
						Pelvis		Other technique					
						Breast							
						Skin							
						Kidney							
						Lung							
						Other: Other location							
						∴	∴	∴		∴			
						Visit	[blank]	[blank]		[blank]	xx.x	xx.x NA	xx.x%
						Summary							

^[1] If Spiral or Conventional CT Scan.

^[2] If lymph node, short axis measurement is recorded.

Note: CT = Computed Tomography, NA = Not Applicable.

Programmer notes: (a) place a “Visit Summary” row following the last line for each time point; (b) leave blank the cells for Baseline Sum of Longest Diameters, Visit Sum of Longest Diameters, and Percent Change from Baseline in each row except for the Visit Summary row described in note (a)

Listing 16.2.6.3
Tumor Evaluations – Non-target Lesions

Treatment Group	Subject ID	Visit	Was radiographic evaluation performed?		Date Performed (Study Day)	Location	Location Description (Position within Organ)	Technique Used	Lesion Status ^[1]
			Yes	No					
Placebo Tarextumab	003-xxx-xxx	Baseline Cycle x			ddmmmyyy (xx)	Pancreas Liver Lymph Nodes Peritoneum Chest Wall Abdomen Pelvis Breast Skin Kidney Lung Other: Other location	Position	MRI Conventional CT Spiral CT PET CT Bone Scan Other: Other technique	CR Non-CR/Non-PD PD Unable to Evaluate

[1] CR = complete response; PD = progressive disease

Listing 16.2.6.4
Tumor Evaluations – New Lesions

Treatment Group	Subject ID	Visit	Was radiographic evaluation performed?		Date Performed (Study Day)	Location	Location Description (Position within Organ)	Technique Used	Lesion Status ^[1]
			Yes	No					
Placebo	003-xxx-xxx	Baseline			ddmmmyyy	Pancreas	Position	MRI	CR
Tarextumab		Cycle x			(xx)	Liver		Conventional	Non-CR/Non-PD
						Lymph Nodes		CT	PD
						Peritoneum		Spiral CT	Unable to Evaluate
						Chest Wall		PET-CT	
						Abdomen		Bone Scan	
						Pelvis		X-Ray	
						Breast		Physical Exam	
						Skin		Other: Other technique	
						Kidney			
						Lung			
						Bone			
						CNS			
						Other: Other location			

[1] CR = complete response; PD = progressive disease

Listing 16.2.6.5
Tumor Assessments (RECIST Overall Response)

Treatment Group	Subject ID	Visit	Response Date (Study Day)	Target Lesion Response ^[1]	Target Lesion Response ^[1]	New Lesions	Overall Response Assessment ^[1]	If Overall Response is Progressive Disease, was it non-radiographic clinical progression?
Placebo Tarextumab	003-xxx-xxx	SCREENING CYCLE X DAY X	ddmmmyyy (xx)	CR PR SD PD Unable to Evaluate: Reason Not Evaluated	No Lesions at Baseline CR PR SD PD Unable to Evaluate: Reason Not Evaluated	Yes No	CR PR SD PD PD Not Evaluated	Yes No

^[1] CR = complete response; PR = partial response; SD = stable disease; PD = progressive disease

Treatment Group	Subject ID	RECIST v1.1 Assessment		PFS ^[2]		OS ^[3]		DOR ^[4]	
		Best Tumor Response	Objective Response ^[1]	Censored	Days	Censored	Days	Censored	Days
Placebo	003-xxx-xxx	CR PR SD PD NE	Yes No	Yes No	xxx	Yes No	xxx	Yes No	xxx
Tarextumab									

Note: CR = complete response; PR = partial response; SD = stable disease; PD = progressive disease; NE = Not Evaluated.

^[1] Best response of CR or PR.

^[2] Progression-Free Survival (PFS) = Date of Documentation of Death/Progression – Randomization Date + 1. Subjects who had not experienced death or progression by their last contact were censored at the time of their last radiographic response assessment. Subjects lacking a radiographic response assessment after randomization who do not progress or die have their event time censored on the date of randomization with duration of 1 day.

^[3] Overall Survival (OS) = Date of Documentation of Death – Randomization Date + 1. Subjects who had not experienced death by their last contact were censored at the time. Subjects lacking data after randomization who do not die have their event time censored on the date of randomization with duration of 1 day.

^[4] Duration of Response (DOR) = Date of Documentation of Death/Progression – Date of First Partial (PR) or Complete Response (CR) + 1. Patients who discontinue the study without disease progression or death while on study are censored on the date of the last on study tumor assessment documenting the absence of progressive disease. Patients lacking a tumor assessment after first dose who do not progress or die while on study have their event time censored on the date of first dose with duration of 1 day.

**OncoMed Pharmaceuticals, Inc.
59R5-003 (Phase 2)**

Page 1 of x

**Listing 16.2.21
End of Treatment**

Treatment Group	Subject ID	Study Drug		Etoposide		Platinum Therapy	
		Date of Last Dose (Study Day)	Primary Reason for Ending	Primary Associated AE	Date of Last Dose (Study Day)	Primary Reason for Ending	Primary Associated AE
Placebo Tarextumab	003-xxx-xxx	ddmmmyyy (xx)	Lost to follow-up Withdrawal of consent/Patient Decision Death Adverse Event Disease progression Investigator decision based on patient's best interest Study Terminated by OncoMed Other: Other term	Adverse Event #xx: AE term	ddmmmyyy (xx)	Lost to follow-up Withdrawal of consent/Patient Decision Death Adverse Event Disease progression Investigator decision based on patient's best interest Study Terminated by OncoMed Other: Other term	Adverse Event #xx: AE term

OncoMed Pharmaceuticals, Inc.
59R5-003 (Phase 2)

Listing 16.2.7.1
Adverse Events
Part 1 of 2

Page 1 of x

Treatment Group	Subject ID	AE #	Verbatim Term // MedDRA Preferred Term // System Organ Class	Onset Date (Study Day)	End Date (Study Day)	On-going	Severity (CTCAE V4.02 Grade)	Treatment of Event	Infusion Reaction	Outcome	Caused by Study Drug		Serious Event	
											Yes	No	Yes	No
Placebo	003-xxx-x	xx	Verbatim Term // MedDRA Preferred Term // System Organ Class	ddmmmyyy (xx)	ddmmmyyy (xx)	Yes	x	None Medication Non-Drug Treatment Hospitalization	Yes	Recovered/Resolved without sequelae Recovered/Resolved with sequelae Not Recovered/Not Resolved Fatal Unknown	Yes	No	Yes	No
Tarextumab	xx				y (xx)	No								

<second part of listing>

OncoMed Pharmaceuticals, Inc.
59R5-003 (Phase 2)

Listing 16.2.7.1
Adverse Events
Part 2 of 2

Page 1 of x

Treatment Group	Subject ID	AE #	Relationship to			Initial Action Taken with			Action Taken with		
			Tarextumab	Etoposide	Platinum Therapy	Tarextumab	Etoposide	Platinum Therapy	Tarextumab	Etoposide	Platinum Therapy
Placebo	003-xxx-xxx	xx	Related	Related	Not Related	None	None	None	None	None	None
Tarextumab			Not Related	Not Related	Related	Dose Reduced	Dose Reduced	Dose Reduced	Dose Reduced	Dose Reduced	Dose Reduced
						Dose Delayed	Dose Delayed	Dose Delayed	Dose Delayed	Dose Delayed	Dose Delayed
						Infusion	Infusion	Infusion	Infusion	Infusion	Infusion
						Interrupted	Interrupted	Interrupted	Interrupted	Interrupted	Interrupted
						Withdrawn	Withdrawn	Withdrawn	Withdrawn	Withdrawn	Withdrawn
						Not Applicable	Not Applicable	Not Applicable	Not Applicable	Not Applicable	Not Applicable

